1.1 Study design

This is a multi-center, open-label PASS to evaluate the effect of LysaKare[®] infusion on serum potassium levels in GEP-NET patients eligible for Lutathera[®] treatment. Eligible patients will be admitted to the in-clinic unit to be dosed with LysaKare[®] solution for infusion of 1,000 mL, which is administered intravenously over a period of 4 hours. Before the infusion (at 0 h time point), a set of baseline tests will be performed. During and after the infusion, patient condition will be monitored for evaluation of any adverse events (AEs). The main purpose of the study is to assess the effect of LysaKare[®] administration on serum potassium concentration in GEP-NET patients eligible for Lutathera[®] treatment.

As per protocol version 01, approximately 45 patients (to have at least 25 patients evaluable for the primary endpoint) with GEP-NET will be enrolled to receive one infusion with LysaKare® to systematically assess the effect of LysaKare® administration on potassium blood level concentration up to 24 h compared to baseline.

The study schedule for each patient consists of a screening period followed by an infusion day with an optional overnight in-clinic stay, and a follow up call as described in Figure 1-1.

The primary analysis is planned to be performed after the last enrolled patient has completed the follow-up phone contact after LysaKare[®] infusion.

AP amendment		CAAA001A124
igure 1-1 Study des		
Screening Phase	Infusion Day	Follow-up
Within 7 days prior	Optional overnight	48 h post infusion
to infusion	stay 0-24 h	
Population	LysaKare solution of	Telephone call to
N=45	1000mL administered	follow up on AEs
Open-label	intravenously for 4	resolution
Key Inclusion	in the second seco	Additional visits or
 SSR-positive GEP- 	Laboratory parameters	assessments may be
NET patients	checked at 0h, 2h, 4h,	conducted if required
eligible for treatment	6h, 8h, 12h and 24 h.	per Investigator's
with Lutathera®		clinical judgement
	Vital signs measured	
Key Exclusion	and ECG recorded at	
Pre-existing	pre-defined time	
hyperkalaemia	points	
 Instances when 		

1.2 Study objectives, endpoints and estimands

safety profile

Objectives and related endpoints are described in Table 1-1 below.

Table 1-1Objectives and related endpoints

Objectives	Endpoints	
Primary objective	Endpoint for primary objective	
To assess the effect of LysaKare® administration on serum potassium concentration in GEP-NET patients eligible for Lutathera® treatment	Change in serum potassium levels at specified time points after LysaKare [®] Intravenous (IV) administration compared to baseline.	
Secondary objective	Endpoints for secondary objective(s)	
To characterize the safety profile on LysaKare [®] infusion in GEP-NET patients eligible for Lutathera [®] treatment without co-administration of Lutathera [®]	 Incidence of LysaKare[®] related AEs Changes in vital signs and Electrocardiogram (ECG) parameters Change in laboratory parameters 	

1.2.1 Primary estimand

recommended

The primary clinical question of interest is: What is the effect of LysaKare[®] administration on serum potassium levels in Gastroenteropancreatic neuroendocrine tumors (GEP-NET) patients eligible for Lutathera[®] treatment regardless of treatment discontinuation or interruption for any reason?

Advanced Accelerator Applications,	Confidential	Page 8 of 27
A Novartis company		
SAP amendment		CAAA001A12401

The justification for the primary estimand is that it will capture the effect on serum potassium concentration that would be seen when LysaKare[®] administration is given to reduce renal radiation exposure in GEP-NET patients eligible for Lutathera[®] treatment.

The primary estimand is described by the following attributes:

- 1. The target population comprises male and female patients who are 18 years or older diagnosed with SSR positive GEP-NET and eligible for treatment with Lutathera[®], who received LysaKare[®].
- 2. **The primary variable** is the change in serum potassium concentration from baseline to 2, 4, 6, 8, 12, and 24 hours after beginning of LysaKare[®] administration.
- 3. The treatment of interest is LysaKare[®] solution administered intravenously over a period of four hours.
- 4. **The intercurrent event** of interest is treatment interruption or discontinuation for any reason. This intercurrent event is ignored (treatment policy strategy).
- 5. **The summary measure** is the mean change with associated 95% Confidence interval (CI) in serum potassium levels from baseline to 2, 4, 6, 8, 12 and 24 hours after beginning of LysaKare[®] administration.

1.2.2 Secondary estimand(s)

Not applicable.

2 Statistical methods

2.1 Data analysis general information

All analyses will be performed by Novartis. SAS version 9.4 or later software will be used to perform all data analyses and to generate tables, figures and listings.

Data included in the analysis

The analysis cut-off date for the primary endpoint analysis is defined as the date when all enrolled patients will have completed the phone call to follow-up on AEs.

All statistical analyses will be performed using all data collected in the database up to the data cut-off date. All data with an assessment date or event start date (e.g., start date of an AE) prior to or on the cut-off date will be included in the analysis. Any data collected beyond the cut-off date will not be included in the analysis and will not be used for any derivations.

All events with start date before or on the cut-off date and end date after the cut-off date will be reported as 'ongoing'. The same rule will be applied to events starting before or on the cut-off date and not having a documented end date. This approach applies, in particular, to AEs and concomitant medication reports. For these events, the end date will not be imputed and therefore will not appear in the listings.

Advanced Accelerator Applications,	Confidential	Page 9 of 27
A Novartis company		
SAP amendment		CAAA001A12401

General analysis conventions

Pooling of centers: Unless specified otherwise, data from all study centers will be pooled for the analysis. However, if any center enrolls a large number of patients, a subgroup analysis by centers will be considered. For the subgroup analysis, lower enrolling centers will be pooled.

Qualitative data (e.g., gender, race (where applicable), etc.) will be summarized by means of contingency tables; a missing category will be included as applicable. Percentages will be calculated using the number of patients in the relevant population as the denominator.

Quantitative data (e.g., age, body weight, etc.) will be summarized by appropriate descriptive statistics (i.e., mean, standard deviation, median, minimum, maximum, and quartiles [where appropriate]).

2.1.1 General definitions

Study treatment

The study treatment, used throughout the protocol and SAP, will refer to the solution of LysaKare[®] administered intravenously. Only one infusion will be given in the treatment phase of the trial.

Date of administration of study treatment

The date and time of administration of study treatment is derived as the start date and time of the infusion. The date and time of administration of study treatment will also be referred as *start of study treatment*.

Study day

The study day describes the day of the event or assessment date, relative to the reference start date.

The study day is defined as:

- The date of the event (visit date, onset date of an event, assessment date, etc.) reference start date + 1 if event is on or after the reference start date.
- The date of the event (visit date, onset date of an event, assessment date, etc.) reference start date if event precedes the reference start date.

The reference start date for all assessments (e.g., AE onset, laboratory abnormality occurrence, vital sign measurement, etc.) is the start of study treatment.

Time units

A year length is defined as 365.25 days. A month length is 30.4375 days (365.25/12). If duration is reported in months, duration in days will be divided by 30.4375. If duration is reported in years, duration in days will be divided by 365.25.

Advanced Accelerator Applications,	Confidential	Page 10 of 27
A Novartis company		
SAP amendment		CAAA001A12401

Baseline

For safety evaluations, the last available assessment on or before the date of start of study treatment is defined as "baseline" assessment.

For cases where time of assessment is captured (e.g., pre-dose ECG, laboratory assessments), the last available assessment before the treatment start date/time is used for baseline.

In rare cases where multiple measurements meet the baseline definition, with no further flag or label that can identify the chronological order, then the following rule should be applied: For ECGs or vital signs, the last value will be considered as baseline.

For the assessment of change in electrolytes and blood gas parameters, the baseline is defined as the assessment 0 hr (i.e., Pre-dose).

If participants have no value as defined above, the baseline results will be considered missing.

On-treatment assessment/event and observation periods

For AE reporting the overall observation period will be divided into three mutually exclusive segments:

- 1. *pre-treatment period*: from day of patient's sign informed consent to the day and time before administration of study treatment.
- 2. *on-treatment period*: from date and time of administration of study treatment to 30 days after date of last administration of study treatment.
- 3. *post-treatment period*: starting at day 31 after administration of study treatment.

If dates are incomplete in a way that clear assignment to pre-, on-, and post-treatment period cannot be made, then the respective data will be assigned to the on-treatment period. Refer to Section 5.1.2 for imputation rules concerning AE start and stop dates.

Safety summaries (tables, figures) include only data from the on-treatment period with the exception of baseline data which will also be summarized where appropriate (e.g., change from baseline summaries). In addition, a separate summary for death including on treatment and post treatment deaths will be provided. In particular, summary tables for AEs will summarize only on-treatment events, with a start date during the on-treatment period (*treatment-emergent* AEs).

However, all safety data will be listed and those collected during the pre-treatment and post-treatment period will be flagged.

Windows for multiple assessments

For the definition of time windows in the treatment phase, refer to the study protocol Section 8.4.2 and Table 8-2 of the Protocol. During the Treatment Phase (infusion day): a time window of +/-5% (equal to 3 min/h) is permitted for study assessments at 2 h, 4 h, 6 h, 8 h, 12 h. A time window of +/-2 hours is accepted for the 24-hour assessments. Study assessments captured outside of the time window will still be used in any analyses and will be captured as a minor protocol deviation.

In order to summarize physical exam, vital sign, ECG, laboratory collected over time (including unscheduled visits), the assessments will be time slotted. The following general rule will be

Advanced Accelerator Applications,	Confidential	Page 11 of 27
A Novartis company		
SAP amendment		CAAA001A12401

applied in creating the assessment windows: If more than one assessment is done within the same time window, the assessment performed closest to the target date will be used. If two assessments within a time window are equidistant from the target date, then the earlier of the two assessments will be used.

If multiple assessments occur on the same date, then the worst-case result will be used. Data from all assessments (scheduled and unscheduled), including multiple assessments, will be listed.

The last contact date is defined as when the enrolled patient has completed the follow-up phone contact 48 hours after LysaKare[®] infusion. The cut-off date will not be used for last contact date, unless the patient was seen or contacted on that date. No data post cut-off date will be used. Completely imputed dates (e.g., the analysis cut-off date programmatically imputed to replace the missing end date of a dose administration record) will not be used to derive the last contact date.

2.2 Analysis sets

Enrolled set

The enrolled set consists of all patients who signed informed consents and participated in the screening phase of the study.

Safety set

The safety set (SAF) comprises all patients who received any administration of the LysaKare[®] infusion in the study.

The safety set will be used for all analyses in this study, whereas the primary endpoint analysis is further restricted to an evaluable subset based on the following specification.

Evaluable set

Evaluable set comprises all patients who received any volume of the LysaKare® infusion and provided at least 2 potassium levels measured from serum: pre-dose value and at least one post-dose value from the post-treatment window where the acute serum potassium changes are expected (between 4 and 8 hours).

2.2.1 Subgroup of interest

Potassium levels as well as key safety (all AEs, AEs with suspected relationship to study treatment and SAEs) analyses will be repeated in the following subgroups:

- Age: 18-64 years vs. \geq 65 years
- Gender : Male vs. Female
- Race: Asian vs. Black or African American vs. White vs. Other (only subgroups with at least 5 patients)
- Center: depending on whether there is any high recruiting center (only centers with at least 10 patients).

Advanced Accelerator Applications,	Confidential	Page 12 of 27
A Novartis company		
SAP amendment		CAAA001A12401

• Creatinine Clearance: < 60ml/min vs. ≥60- <90 ml/min vs. ≥ 90 ml/min (only subgroups with at least 5 patients).

The objective for carrying out these subgroup analyses is to identify potential safety issues that may be limited to a subgroup of patients, or safety issues that are more commonly observed in a subgroup of patients.

2.3 Patient disposition, demographics and other baseline characteristics

The SAF will be used for all baseline and demographic summaries and listings unless otherwise specified. No inferential statistics will be provided.

2.3.1 Patient disposition

Enrollment by country and center will be summarized for all screened patients. The number and percentage of patients included in the SAF will be presented. The number (%) of screened and not-treated patients and the reasons for screening failure will also be displayed. The number (%) of patients in the SAF who completed the study follow-up period, who discontinued the study follow-up and the reason for discontinuation will be presented.

Protocol deviations

The number (%) of patients in the SAF with any major protocol deviation will be tabulated by deviation category (as specified in the study Data Management Plan). All protocol deviations will be listed.

Analysis sets

The number (%) of patients in each analysis set (defined in Section 2.2) will be summarized.

2.3.2 Demographics and other baseline characteristics

Basic demographic and background data

All demographic and baseline disease characteristics data will be summarized and listed. Categorical data (e.g., gender, age groups: <65 and \geq 65 years, race, ethnicity) will be summarized by frequency counts and percentages; the number and percentage of patients with missing data will be provided. Continuous data (e.g., age, weight, height, body mass index [BMI]) will be summarized by descriptive statistics (N, mean, median, standard deviation, 25th and 75th percentiles, minimum and maximum). BMI (kg/m2) will be calculated as weight[kg] / (height[m2]) using weight at Baseline.

Diagnosis and extent of cancer

Summary statistics will be tabulated for diagnosis and extent of cancer. This analysis will include the following: time since initial GEP-NET tumor diagnosis, primary site of cancer, tumor, node, metastasis (TNM) criteria at screening date, disease stage, time since most recent

Advanced Accelerator Applications,	Confidential	Page 13 of 27
A Novartis company		
SAP amendment		CAAA001A12401

relapse/progression, GEP-NET grade according to Ki-67 index, presence of metastases at time of screening, and number and type of metastatic sites involved.

Medical history

Medical history and ongoing conditions will be summarized. Separate summaries will be presented for ongoing and historical medical conditions. The summaries will be presented by primary system organ class (SOC), and preferred term (PT). Medical history and current medical conditions will be coded using the Medical Dictionary for Regulatory Activities (MedDRA) terminology. The MedDRA version used for reporting will be specified in the CSR and as a footnote in the applicable tables/listings.

Other

All data collected at baseline will be listed as appropriate.

2.4 Treatments (study treatment, rescue medication, concomitant therapies, compliance)

2.4.1 Exposure to study treatment

Duration of exposure to study treatment will be derived as follows:

Duration of exposure to study treatment (*hours*) = End time of LysaKare[®] infusion – Start time of LysaKare[®] infusion.

Duration of exposure, total duration of dose interruption as well as the actual total volume of the LysaKare[®] infusion, will be summarized. Duration of exposure will be categorized into time intervals (<1 hour. 1- <2 hours, 2- <3 hours and 40 minutes, 3 hours 40 minutes- 4 hours and 20 minutes, and > 4 hours and 20 minutes); frequency counts and percentages will be presented for the number (%) of subjects in each interval. Actual total volume will be categorized into volume intervals (< 250 mL, 250-499 mL, 500-749 mL, 750-899 mL, 900-1000 mL, > 1000 mL); frequency counts and percentages will be presented for the number (%) of subjects who have dose discontinuations prior to receiving at least 900 mL of LysaKare[®] will be summarized as well as the number of subjects with dose interruptions, with the associated reasons. The number (%) who received an antiemetic before or during LysaKare[®] infusion will be presented.

The safety set will be used for all summaries and listings of study treatment.

2.4.2 **Prior**, concomitant and post therapies

Prior and concomitant anti-cancer therapy

The number and percentage of patients who received any prior anti-neoplastic medications, prior anti-neoplastic radiotherapy or underwent prior anti-neoplastic surgery will be summarized. Prior anti-neoplastic medications will be summarized by lowest ATC class, and PT.

Advanced Accelerator Applications,	Confidential	Page 14 of 27
A Novartis company		
SAP amendment		CAAA001A12401

Similarly, the number and percentage of patients who received any concomitant anti-neoplastic medications, concomitant anti-neoplastic radiotherapy or underwent any concomitant anti-neoplastic surgery will be summarized. Concomitant anti-neoplastic medications will be summarized by lowest ATC class, and PT.

Separate listings will be produced for prior and concomitant anti-neoplastic medications, radiotherapy, and surgery.

Anti-neoplastic medications will be coded using the World Health Organization (WHO) Drug Reference List (WHO-DRL). Details regarding WHO-DRL version will be included in the footnote in the tables/listings.

Concomitant therapy

Concomitant therapy is defined as all interventions (therapeutic treatments and procedures) other than the study treatment administered to a patient coinciding with the study treatment period. Concomitant therapy includes medications (other than study treatment) starting on or after the start date of study treatment or medications starting prior to the start date of study treatment and continuing after the start date of study treatment. Prior therapy includes medication of which the start date and end date both prior to the start date of study treatment.

Concomitant medications will be coded using the WHO-DRL dictionary that employs the WHO Anatomical Therapeutic Chemical (ATC) classification system and summarized by lowest ATC class and PT using frequency counts and percentages.

Surgical and medical procedures will be coded using MedDRA and summarized by SOC and PT.

All concomitant therapies will be listed. Any concomitant therapies starting and ending prior to the start of study treatment will be flagged in the listing. The safety set will be used for all concomitant medication tables and listings.

2.5 Analysis supporting primary objective(s)

The primary objective of the study is to evaluate the effect of LysaKare[®] administration on serum potassium concentration in GEP-NET patients eligible for Lutathera[®] treatment.

2.5.1 **Primary endpoint(s)**

The primary endpoint of the study is change in the serum potassium levels at specified time points after LysaKare® IV administration compared to baseline. The primary analysis will be performed on the Evaluable Set after the last enrolled patient has completed the follow-up phone contact after LysaKare® infusion.

Potassium testing will be performed on the infusion day at the following timepoints: 0 h (before the start of the infusion), 2 h, 4 h, 6 h, 8 h, 12 h, and 24 h (after the start of the infusion).

2.5.2 Statistical hypothesis, model, and method of analysis

The study is descriptive in nature, and no hypothesis will be tested for study endpoints. The study will analyze and describe various parameters related to serum potassium concentration,

Advanced Accelerator Applications,	Confidential	Page 15 of 27
A Novartis company		
SAP amendment		CAAA001A12401

including mean change, maximum change, and time to the maximum change. In particular, maximum change and time to the maximum change will be summarized by descriptive statistics (N, median, minimum, maximum, and interquartile range).

The mean (+/- SD) concentration-time profiles for serum potassium concentration by treatment over time will be displayed graphically for the Evaluable set on the linear view.

To visualize the evolution of potassium level for each patient a spaghetti plot will be displayed along with a box plot to see the summary of potassium levels at each time point.

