4.1 Rationale for study design

This is a category 3 Post-Authorization Safety Study (PASS) following the European Medicines Agency (EMA) marketing authorization of LysaKare[®] 25 g/ 15 g solution for infusion. LysaKare[®] is indicated for reduction of renal radiation exposure during peptide-receptor radionuclide therapy (PRRT) with lutetium (177Lu) oxodotreotide in adults. The marketing authorization was granted based on literature data from similar amino acids solutions (well established use application).

The purpose of the study is to evaluate the effect of LysaKare[®] administration on serum potassium levels.

The primary endpoint of this study is the change in serum potassium levels after LysaKare[®] IV administration compared to baseline. The selection of this endpoint is supported by findings of a study, which assessed hourly potassium changes (at 0, 0.5, 1, 2, 4 and 5 hours) measured in 11 patients treated with 2.5% Lys-Arg solution (Krenning 2000). Peak serum potassium levels were observed at 2-4 h post-baseline, the mean baseline level was 4.2 mmol/L, mean increase at 2 h was 0.6 mmol/L and at 4 h it was 0.9 mmol/L (SD=0.3) the maximum increase was 1.5 mmol/L. The mild increase in potassium levels did not manifest in any safety issues or clinically significant events.

The study has a descriptive nature, and no hypothesis will be tested for the study endpoints. The study will describe and analyze various parameters related to potassium concentration, including mean change, maximum change, time to the maximum change, and the overall dynamics of the concentration curve during and after the LysaKare[®] infusion. In order to calculate the sample size for the study, it was assumed that the mean change in potassium levels over baseline values is less than 1.1 mmol/L (a safety margin of 0.2 mmol/L has been added to the mean increase of 0.9 mmol/L observed in the previous study at 4 h).

AA solutions have fast plasma elimination kinetics with AA levels returning to baseline by 6 hours post-dose (Tangphao 1999, Irving 1986). Serum potassium levels after amino acid administration normally return to near baseline within 24 hours (Giovacchini 2011, Lapa 2014a, Lapa 2014b, Krenning 2000). Therefore, the time points for potassium level assessments in this study extend from 0 h to 24 h, and the follow up is conducted at 48 hours post dose.

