12.1 Analysis sets

The Safety Set (SAF) comprises all subjects who received any volume of the LysaKare[®] infusion in the study.

The Safety Set will be used for the analyses below, whereas the primary endpoint analysis is further restricted to an evaluable subset based on the following specification.

Potassium levels are evaluable for the primary endpoint only if there are at least 2 values measured from serum: one from baseline and one (minimum) from the post-treatment window where the acute serum potassium changes are expected. Therefore, the Primary Analysis Evaluable Set comprises of subjects who received any volume of the LysaKare[®] infusion and have both pre-dose and at least one post-dose (between 4 and 8 hours) potassium levels measured from serum.

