12.4.2 Statistical model, hypothesis, and method of analysis

The study is descriptive in nature, and no hypothesis will be tested for study endpoints. The study will analyze and describe various primary variables related to potassium concentration, including mean change, maximum change, time to the maximum change, and the overall dynamics of the concentration curve during and after the LysaKare[®] infusion.

The primary endpoint analysis will be conducted on the Primary Analysis Evaluable Set.

In particular, maximum change and time to the maximum change will be summarized by descriptive statistics (N, median, minimum, maximum, and interquartile range). The mean (+/-SD) concentration-time profiles for serum potassium will be displayed graphically on the linear view.

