2.5.4 Handling of missing values not related to intercurrent event

There will be no replacement of missing data not related to intercurrent events.

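### Maximum change and time to maximum are summarised on a set that admits patients whose only post-dose serum value falls after the expected peak, which lowers the typical maximum whenever such patients occur

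*SAP*

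**What the plan says.** - **Summary.** SAP 2.5.2: "maximum change and time to the maximum change will be summarized by descriptive statistics". The statistics are N, median, minimum, maximum and interquartile range. Protocol 12.4.2 plans the same and counts both quantities among its primary variables.
- **Set.** SAP 2.5.2 names the Evaluable Set only for the profile plot. Its use for these summaries follows from SAP 2.5.1, "The primary analysis will be performed on the Evaluable Set", and Protocol 12.4.2, "The primary endpoint analysis will be conducted on the Primary Analysis Evaluable Set".
- **Entry rule.** SAP 2.2 asks that the patient "provided at least 2 potassium levels measured from serum": the pre-dose value and one between 4 and 8 h. Protocol 12.1 has the same rule; patients must "have both pre-dose and at least one post-dose (between 4 and 8 hours) potassium levels measured from serum". Neither the 2 h nor the 4 h sample is required.
- **Missing values.** SAP 2.5.4: "There will be no replacement of missing data not related to intercurrent events". Protocol 12.4.3 also rules out replacement.
- **Expected course.** Protocol 4.1: "Peak serum potassium levels were observed at 2-4 h post-baseline". Protocol 1.1 describes a plateau or decrease at 5 h, then a return to baseline.

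**The concern.** A mean at one time point tolerates patients who lack a sample there. A maximum over a patient's own samples does not: losing samples near the peak can only lower it. Under the entry rule, a patient with serum at 0 h and 8 h alone is evaluable, contributes the 8 h change as the maximum, and contributes 8 h as its time. Nothing in either document sets a minimum number of samples for these two summaries or requires one near the expected peak.

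The situation is plausible. The Protocol Amendment 01 rationale reports non-serum samples in 13 of the first 30 patients and says those values cannot serve the primary endpoint. SAP 2.5.6 plans an analysis that adds post-infusion values from any source while excluding patients whose pre-treatment value was whole blood, which implies that some mixed profiles are foreseen.

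At stake is the description of the typical peak rise and its timing, two of the parameters the study says it will describe.

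**Working it through.** **Inputs from the documents.** Mean change 0.6 mmol/L at 2 h and 0.9 at 4 h, SD 0.3, from 11 patients sampled up to 5 h (Protocol 4.1 and 12.8; SAP 3). Minimum evaluable N 25, planned enrolment about 45.

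**Step 1: the plan's own figures.** Half-width = t(0.975, n-1) × 0.3 / √n.
- n = 38: 2.026 × 0.3 / 6.164 = 0.0986, stated as 0.099.
- n = 25: 2.064 × 0.3 / 5 = 0.1238, total length 0.2477, stated as 0.25.

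Both reproduce. The documents give no planning figure for the maximum or its time.

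**Step 2: direction.** If S is a subset of the scheduled times, the maximum over S cannot exceed the maximum over all of them. This needs no assumption.

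**Step 3: size for one patient.** Changes were simulated as multivariate normal. Assumed, because the documents do not give them:
- SD 0.3 at every time point, and within-patient correlation 0.3 to 0.9;
- means at 6/8/12/24 h of 0.80/0.65/0.35/0.05 (slow), 0.70/0.45/0.20/0 (mid) or 0.50/0.20/0.05/0 (fast).

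Results:
- Full profile: mean observed maximum 0.90-1.04 mmol/L.
- 8 h only: 0.20-0.65, below the patient's full-schedule maximum in 88-100% of cases.
- 6 h only: 0.50-0.80.
- 4 h only: 0.90, an average shortfall of 0.00-0.14.

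The problem therefore lies with patients who have serum at 6 h only, at 8 h only, or at both but not at 4 h.

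**Step 4: size for the set.** k of 25 patients have only the 8 h value; correlation 0.6. Entries are averages over simulated trials.

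| Profile | Median, k=0 | k=1 | k=3 | k=5 | Lower quartile, k=0 → 5 | Largest value, k=0 → 5 | Upper quartile of time (h), k=0 → 5 |
|---|---|---|---|---|---|---|---|
| Slow | 0.98 | 0.97 | 0.95 | 0.93 | 0.81 → 0.73 | 1.53 → 1.51 | 5.8 → 7.2 |
| Mid | 0.95 | 0.93 | 0.90 | 0.87 | 0.77 → 0.65 | 1.51 → 1.48 | 4.6 → 6.0 |
| Fast | 0.92 | 0.91 | 0.87 | 0.83 | 0.74 → 0.57 | 1.49 → 1.47 | 4.0 → 4.6 |

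**Step 5: other profiles.** Two linear declines from 0.9 at 4 h were added, reaching baseline at 24 h or at 12 h, with correlations 0.3, 0.6 and 0.9. Over all five profiles the median maximum falls by about 0.01 mmol/L when 4% are 8 h-only, 0.02-0.04 at 10% and 0.04-0.09 at 20%.

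In the slow, mid and fast profiles, median time to maximum stays at 4 h at 10% in all nine settings, and at 20% in seven of nine. The exceptions are slow profiles, where it becomes 6 h. With the linear return to 24 h, the flattest profile tried, it can reach 6 h at 10% or below when correlation is 0.3 or 0.6.

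**Step 6: possible share.** If all 13 known affected patients were evaluable with late serum only, and the other 32 of 45 were complete, the share is 13/45 = 29%.

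**The case against.** The strongest reply is that the affected patients may be few or absent. No passage reports an evaluable patient with serum only at 6 h or 8 h. Patients remain in clinic through the 12 h sample, little drop-out is expected, and Protocol version 01 requires serum at every electrolyte time point with one sampling method throughout. The amendment counts affected patients, not time points. Spaghetti plots and laboratory listings will make incomplete profiles visible. All of this stands, and it limits the size of the point.

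It does not remove it. The plots do not alter the table. The mixed model in SAP 2.5.5 estimates change by time point, not each patient's maximum. The all-source analysis in SAP 2.5.6 fills gaps with values the SAP itself expects to read high.

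Four stronger readings are tempting, and the documents do not support them.
- **That the maximum will be understated in this trial.** That needs a count of late-only patients, which is not given.
- **That 13 of 30 (43%) shows a share of 40% or more is in prospect.** At planned enrolment the known deviations give at most 29%, under the conditions in Step 6.
- **That time to maximum is generally distorted.** The planned location statistic is the median, which usually stays at 4 h.
- **That the hyperkalaemia assessment is compromised.** Potassium is categorised by normal range and CTC grade at each time point in the Safety Set whatever the sample source (SAP 2.5.6). Hyperkalaemia is the adverse event of special interest (SAP 2.7.1.1) and has an exact interval (SAP 5.4.2). The primary estimand is mean change by time point. None of these depends on this summary.

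**Conclusion.** The point holds as a conditional one. For any Evaluable Set patient without serum near the expected peak, the recorded maximum change is at most the full-schedule maximum and probably below it, and its time reflects which sample was valid. The direction is certain. The size depends on an unstated number of patients and on assumed potassium levels after 5 h, where the historical sampling ended.

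The falls in the median found above, about 0.01 mmol/L at 4%, 0.02-0.04 at 10% and 0.04-0.09 at 20% with only an 8 h value, compare with the plan's own half-width of 0.12 for the 4 h mean at N = 25. The lower quartile falls more. This merits a short pre-lock clarification and does not threaten the primary estimand.

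**What to change.** In SAP 2.5.2, before database lock:
- Base the main summary of maximum change and time to maximum on Evaluable Set patients with serum values at 0 h, 4 h and at least one of 6 h or 8 h.
- Report N by sampling pattern.
- Show the all-Evaluable-Set summary alongside, labelled as a lower bound for patients without a 4 h value, so that no large rise is dropped.
- Leave the mean changes by time point on all available serum values.

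Requiring the 2 h sample as well would be too strict. In the slow, mid and fast profiles at correlation 0.6, its absence lowers the maximum by only 0.006-0.015 mmol/L on average. The proposed rule shrinks the shortfall without abolishing it: in the same profiles, a patient with only 4 h and 8 h values loses 0.02-0.06 on average, against 0.33-0.72 for one with only 8 h.

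The cost is a somewhat smaller N for the main version of these two summaries and one extra table column. If every evaluable patient meets the condition, the results do not change.
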